###### 5.1.1.1.2 Study Treatments

The following treatment groups are defined for this study:

- AGN-199201 [REDACTED] AGN-190584 [REDACTED]
- AGN-199201 [REDACTED] + AGN-190584 [REDACTED]
- AGN-199201 [REDACTED] + AGN-190584 [REDACTED]
- AGN-199201 [REDACTED] AGN-190584 [REDACTED]
- Fixed Combo + Fixed Combo [REDACTED]
- AGN-199201 0% + AGN-190584 [REDACTED]
- AGN-199201 [REDACTED] + AGN-190584 [REDACTED]

- AGN-199201 [REDACTED] + AGN-190584 [REDACTED]
- AGN-199201 [REDACTED] + AGN-190584 [REDACTED]
- AGN-199201 [REDACTED] + AGN-190584 [REDACTED]
- AGN-199201 [REDACTED] + AGN-190584 [REDACTED]
- AGN-199201 [REDACTED] + AGN-190584 [REDACTED]
- AGN-199201 [REDACTED] + AGN-190584 [REDACTED]
- AGN-199201 [REDACTED] + AGN-190584 [REDACTED]
- AGN-199201 [REDACTED] + AGN-190584 [REDACTED]
- AGN-199201 [REDACTED] + AGN-190584 [REDACTED]
- AGN-199201 [REDACTED] + AGN-190584 [REDACTED]

The following treatment sequences are defined for this study:

### **5.1.1.1.3 Statistical Methodology**

The methodologies defined below apply as specified to individual endpoints defined in this SAP. When indicated, 95% two-sided confidence intervals and two-sided p-values will be presented.

Individual endpoint analyses may specify exceptions (additions or deletions) to these general definitions.

**Table 5-3 Statistical Methodology**

Methodology		Description
M1	Categorical counts	
 
• Number of subjects in individual categories               
 
○ Subjects with <math>\geq 1</math> qualifying event counted once per individual category
 
 
 

M2	Categorical descriptives	
 
• Number and percentage of subjects in individual categories               
 
○ Subjects with <math>\geq 1</math> qualifying event counted once per individual category
 
 
 
• (Optional) N included if percentage denominator <math>\neq</math> number of subjects in the population (standard percentage denominator).
 

M3	PCS descriptives	
 
• Number and percentage of subjects meeting potentially clinically significant (PCS) criteria               
 
○ Subjects with <math>\geq 1</math> qualifying event counted once per PCS category
 
 
 
• Percentage denominator = number of subjects with non-missing baseline and <math>\geq 1</math> non-missing postbaseline assessment
 
• Unevaluable assessments considered missing
 

M4	Continuous descriptives	
 
• N included, mean, standard deviation (SD), median, minimum, maximum
 
• N included = subjects with non-missing value
 

M5	CFB descriptives	
 
• Continuous descriptives for baseline, postbaseline, and change from baseline (CFB) values
 
• N included = subjects with non-missing values at both baseline and the specified postbaseline analysis visit
 

M6	CFB ANCOVA	
 
• Continuous descriptives and standard error (SE) for baseline, postbaseline, and CFB values
 
• Estimates derived from mixed model for CFB value controlling for factors (pilocarpine dose, oxymetazoline dose) and covariates (baseline UNVA severity, iris color)               
 
○ Least squares (LS) means and standard errors
 
○ P-values from contrast t-test comparing active AGN-199201 treatment groups vs AGN-199201 vehicle
 
 
 
• N included = subjects with non-missing values at both baseline and the postbaseline analysis visit
 

M7	CFB MMRM	
 
• Continuous descriptives and SE for baseline, postbaseline, and CFB values at each analysis visit               
 
○ N included = subjects with non-missing values at both baseline and the postbaseline analysis visit
 
 
 
• Estimates derived from mixed model for CFB value controlling for fixed factors (pilocarpine dose, oxymetazoline dose,), covariates (baseline UNVA severity, iris color), and interactions (pilocarpine dose and oxymetazoline dose interaction), with an compound symmetry covariance matrix               
 
○ LS means and standard errors
 
○ N included = subjects with non-missing values at both baseline and postbaseline analysis visit
 
 
 

M8	CFB figure	
 
• Plot of CFB LS means and SE bars for each treatment group.
 

M9	CFB RS figure	
 
• Plot of CFB response surface in 3 dimension.
 

M10	Responder	
 
• Categorical descriptives for responders and nonresponders               
 
○ Nonresponders include:                   
 
▪ Subjects who do not meet responder criteria
 
 
 
 
 

CFB = change from baseline; ANCOVA = analysis of covariance; ANOVA = analysis of variance.

MMRM = mixed model for repeated measures; RS=response surface

Raw and derived data listings will be provided, and will be fully defined in the table, figure, and data listing specification document.

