
The per protocol (PP) population is defined as all randomized patients who have no significant protocol deviations that affect the primary efficacy variable and complete all study visits. The PP population will be determined prior to database lock. The primary efficacy variable will be analyzed using the PP population on an as-treated basis.

The safety population is defined as all patients who received at least 1 dose of study treatment and will be analyzed as treated. All safety measures will be analyzed using the safety population.

In general, continuous data will be summarized with descriptive statistics (number of patients, mean, standard deviation, median, minimum, and maximum) and will be analyzed using mixed model techniques or 2-sample t-tests (for between-group comparisons) and paired t-tests (for within-group analyses). Categorical variables will be summarized by sample size (N), frequency count and percent, and will be analyzed using Pearson's chi-square test, Fisher's exact test, or Cochran-Mantel-Haenszel (CMH) test.

There will be no imputation of missing data for all analysis.

Efficacy:

The primary efficacy variable is the weighted average change from baseline in UNVA letters in the nondominant eye over two-day dosing periods between hour 1 and hour 10. Baseline will be the hour 0 measure for each dosing period. For the primary efficacy analyses, the weighted average change from baseline will be analyzed by response surface approach using a mixed model with treatment group, dosing period, baseline UNVA, and iris color as fixed effects.

A UNVA responder is defined as a patient with at least a 3 line improvement in mesopic, high contrast, UNVA from baseline (hour 0 of visit 1) at most of the postdose time points in the nondominant eye. The proportion of the UNVA responders will be compared by frequency distribution.

There will be no adjustment for multiple tests.

Detailed descriptions will be documented in analysis plan.

Safety:

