2.2 Clinical Hypotheses

[figure not shown]
At least one concurrently dosed combination of AGN-199201 and AGN-190584 will:

- demonstrate a significant improvement in UNVA over monotherapy with AGN-199201 and monotherapy with AGN-190584 when they are dosed at the same concentrations as the combination
- 2. produce safety and tolerability findings no worse than cumulative findings with AGN-199201 monotherapy and AGN-190584 monotherapy when they are dosed at the same concentrations as the combination

3. Study Design

This study is a phase 2, multicenter, double-masked, parallel-group, randomized sequence, dose response, vehicle-controlled study in patients with presbyopia. Four groups (see Table 1) of different concentrations of AGN-190584 will be used to compare unfixed combinations with AGN-199201 and a fixed combination of AGN-190584 and a fixed combination of AGN-190584 and AGN-199201 solutions dosed in the nondominant eye during 5 dosing periods. For all 4 treatment groups, each dosing period will be once daily for 2 consecutive days, followed by a 7 to 21 day washout before the next 2-day dosing period, until exit after the fifth 2-day dosing period. The study duration will be 39 to 112 days per patient.

Following a screening visit (days -18 to -1) patients will be randomized at a baseline visit (visit 1) in a 1:1:1:1 ratio (stratified by the UNVA at baseline of $\leq 20/80$ and > 20/80) to 1 of the following treatment groups (also summarized in Table 1):

All patients will receive the fixed combination of AGN-199201 and AGN-190584 ophthalmic solutions within one of the 5 dosing periods. Vehicles for AGN-190584, AGN-199201, and the fixed combination ophthalmic solutions all have the same formulation.

Study medication will be administered once daily in each eye during office visits at hour 0 (8 AM \pm 1 hour) for 2 consecutive days during each dosing period. Dosing periods will be separated by a washout period of 14 ± 7 days. Eyes receiving both AGN-199201 and AGN-190584 are to receive a single drop of AGN-199201, followed approximately 5 to 7 minutes later by a single drop of AGN-190584. Eyes receiving the fixed combination of AGN-190584 and AGN-199201 are to receive a single drop of the fixed combination drug, followed approximately 5 to 7 minutes later by a single drop of vehicle. Eyes receiving vehicle alone are to receive 2 drops of vehicle, separated by approximately 5 to 7 minutes. The study design is depicted in Figure 1.

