7.5 Sample Size Calculation

The study consists of 4 parallel groups and 5 sequences of 2-day dosing periods within each group (see Figure 1). Each dosing period is separated by a washout of 14 ± 7 days and each sequence is tested 8 times resulting in 40 patients per group.

The sample size is deemed appropriate to build a response surface model that assesses the efficacy profile of the combination relative to monotherapies.

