**Table 5-15 Mesopic, High Contrast UNVA Analyses**

Endpoint	Description	Timing	Methodology
Average change from baseline in UNVA letters (Primary efficacy variable)	Average change from baseline in UNVA letters  in the nondominant eye over two-day dosing periods between hour 1 and hour 10.	Treatment Period	CFB MMRM  CFB ANCOVA  CFB RS figure CFB figure
[REDACTED]	[REDACTED]	[REDACTED]	[REDACTED]
[REDACTED]	[REDACTED]	[REDACTED]	[REDACTED]
[REDACTED]	[REDACTED]	[REDACTED]	[REDACTED]
[REDACTED]	[REDACTED]	[REDACTED]	[REDACTED]
[REDACTED]	[REDACTED]	[REDACTED]	[REDACTED]

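### The readable SAP p-values for the primary variable compare oxymetazoline doses with vehicle in a model without interaction, so they cannot decide whether any combination beats both monotherapies (Protocol 2.2)

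*SAP*

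**What the plan says.** Protocol 2.2 expects this of at least one combination: "demonstrate a significant improvement in UNVA over monotherapy with AGN-199201 and monotherapy with AGN-190584 when they are dosed at the same concentrations". The concentrations meant are those within that combination. This is a claim about individual combinations, each with two comparators. Protocol 7.3 sets significance at two-sided p ≤ 0.05.

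SAP Table 5-15 assigns four methods to the primary variable, all defined in Table 5-3:

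- **M6 (CFB ANCOVA)** is a mixed model "controlling for factors (pilocarpine dose, oxymetazoline dose) and covariates (baseline UNVA severity, iris color"). No interaction is listed. Its p-values are described as "P-values from contrast t-test comparing active AGN-199201 treatment groups vs AGN-199201 vehicle".
- **M7 (CFB MMRM)** adds "interactions (pilocarpine dose and oxymetazoline dose interaction), with an compound symmetry covariance matrix". Its readable output is LS means and standard errors, with no contrast or p-value.
- **M8** plots LS means with standard-error bars, and **M9** is a "Plot of CFB response surface in 3 dimension".

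The efficacy part of the Protocol Summary says the primary variable "will be analyzed by response surface approach using a mixed model with treatment group, dosing period, baseline UNVA, and iris color as fixed effects". Protocol 7.5 adds: "The sample size is deemed appropriate to build a response surface model that assesses the efficacy profile of the combination relative to monotherapies". Neither names a contrast. SAP 5.1.1.3.1, on study success criteria, says only that type 1 error is not adjusted. Protocol 7.3 lists two-sample and paired t-tests for continuous data in general and ties none of them to a combination-versus-monotherapy comparison.

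**The concern.** The hypothesis and the readable tests address different questions. Without an interaction term, M6 estimates each oxymetazoline effect as an average over four pilocarpine levels, one of which is vehicle. A significant result shows that oxymetazoline adds something on average. It does not show that any one combination beats pilocarpine alone at that combination's own concentration, and it says nothing about beating AGN-199201 alone. A non-significant result does not show that no combination succeeds.

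M7 can supply the missing comparisons. If they are not named before unmasking, 9 combinations × 2 comparators = 18 comparisons are available, and which of them are cited in support of Protocol 2.2 stays open until the data have been seen.

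**Working it through.** **Inputs from the documents.** There are three active oxymetazoline and three active pilocarpine concentrations (Protocol 1.4). That gives 9 unfixed combinations, and 4 × 4 = 16 cells with the vehicles (SAP 4.1). Each group has 40 patients (Protocol 4.1, SAP 5.1.2). Oxymetazoline varies within patients and pilocarpine between patients (Protocol 1.4).

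**The plan's own figures.** SAP 5.1.2: 160 × (1 − 0.10) = 144 completers, or 36 per group. Protocol 4.1: 40 × (1 − 0.125) = 35 per group. Each reproduces, although the two dropout rates differ. Neither document gives an SD, an effect size, a power or a within-patient correlation.

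**Assumptions.** Total SD 1, compound symmetry, ICC r = 0.3, 0.5 or 0.7, fixed-combination records left out, normal tests at two-sided 0.05.

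**1. Standard errors, 40 per group**

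| Contrast | Formula | r = 0.3 | r = 0.5 | r = 0.7 |
|---|---|---|---|---|
| M6, one dose vs vehicle | √[2(1−r)/160] | 0.0935 | 0.0791 | 0.0612 |
| M6, three doses pooled vs vehicle | √[(1−r)(1+1/3)/160] | 0.0764 | 0.0645 | 0.0500 |
| Cell vs AGN-190584 alone (within patient) | √[2(1−r)/40] | 0.1871 | 0.1581 | 0.1225 |
| Cell vs AGN-199201 alone (between patients) | √(2/40) | 0.2236 | 0.2236 | 0.2236 |

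**2. Power of M6 when oxymetazoline helps at only k active pilocarpine levels.** Set the within-patient cell contrast at 80% power, so its noncentrality is 1.96 + 0.84 = 2.80.

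- *Dose-specific M6.* The expected contrast is k/4 of the cell effect and the SE is half the cell SE, so the noncentrality is (k/2) × 2.80 = 1.40, 2.80, 4.20 for k = 1, 2, 3. Power is 29%, 80%, 99%.
- *Pooled M6, all three doses work.* The SE is the cell SE divided by 2.45, so the noncentrality is (k/4) × 2.45 × 2.80 ≈ 1.72, 3.43, 5.15. Power is 40%, 93%, 99.9%.
- *Pooled M6, one dose works.* One third of those values: 0.57, 1.14, 1.72. Power is 9%, 21%, 40%.

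**3. M6 against the truth of Protocol 2.2.** Simulation, 20,000 runs, 36 per group, r = 0.5 (range for r = 0.3 to 0.7 in brackets):

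- Oxymetazoline effect 0.5 SD, pilocarpine nil, so no combination beats oxymetazoline alone. M6 is significant in 100% of trials.
- Each drug alone gives 1.0 SD and combining adds nothing. M6 is significant in 96% (87% to 100%) pooled, or 97% (91% to 100%) for any of three dose contrasts.
- One combination is truly better, by 0.5 SD over pilocarpine alone and 1.5 SD over oxymetazoline alone. M6 is significant in 9% (7% to 12%) pooled, or 33% (25% to 50%) for any dose. Requiring both cell contrasts to be significant, at least one combination passes in 87% (75% to 98%).

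**4. False wins under the paired rule, unadjusted.** Simulation, 200,000 trials, 40 per group, both contrasts significant in the favourable direction, r = 0.3/0.5/0.7:

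- oxymetazoline adds nothing, pilocarpine effect large: 17.8/17.6/17.7%;
- pilocarpine adds nothing, oxymetazoline effect large: 16.3/14.8/13.0%;
- neither works: 3.1/2.5/1.8%.

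The bound for nine independent tests is 1 − 0.975⁹ = 20.4%.

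**The case against.** **Missing text.** The gap falls where this copy is incomplete. In Table 5-15, footnotes 2 and 3 are attached to M7 and M6, and their text is absent. SAP 5.1.1.1.3 lets individual endpoints add to the general definitions, and other rows of Table 5-15 are redacted. A reader might infer that the plan contains no test of a combination against its components. The documents do not support that; the point is limited to what can be read.

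**How many p-values.** A reader might also infer that M6 yields a single overall oxymetazoline p-value. The wording is plural and there are three active doses, so up to three may be meant. SAP 5.1.1.1.2 also uses the term treatment groups for the individual treatment combinations, so cell-level comparisons with pilocarpine alone may have been intended. The additive terms listed for M6 weigh against that reading, and it would cover only half of the hypothesis. Section 3 of the working covers both the pooled and the dose-specific reading; the conclusion is the same.

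**Purpose.** This is phase 2 dose-finding. The readable primary objective is to identify optimum concentrations, the sample size is justified by a response surface, and Protocol 1.4 says the design favours sensitivity to oxymetazoline. M6 and M9 suit that aim, and this part of the objection stands. But Protocol 2.2 claims significance over both monotherapies, and both documents justify the sample size by the combination relative to monotherapies.

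**Transparency.** M7 reports LS means and SEs. If these are given by dose combination, a reader could closely approximate the between-patient contrasts; the within-patient ones also need the covariance. This reduces the risk of selective reporting but does not say which contrasts count.

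**Conclusion.** The concern holds for the readable text and should be fixed; confidence is medium because of the missing footnotes. The M6 p-values, whether three or one, cannot decide Protocol 2.2. M6 is not a poor analysis as such: for a general oxymetazoline effect it is more powerful than a cell contrast, and it is weak only when the benefit is confined to one pilocarpine level or, if pooled, to one dose. Nor is the trial unable to answer its question, since M7 as planned contains what is needed.

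The power figures rest on the assumed compound symmetry and an effect that is equal where present and absent elsewhere; the simulated figures rest also on the assumed effect sizes and ICC range. That M6 includes no comparison with AGN-199201 alone rests on none of these.

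**What to change.** In the SAP, before unmasking, specify from M7 with both doses categorical, for each of the 9 unfixed combinations:

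1. the contrast with AGN-190584 alone at the same concentration (within patient);
2. the contrast with AGN-199201 alone at the same concentration (between patients).

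Call a combination better than its components only if both are significant in its favour. Keep M6 and the response surface for dose-finding and as supportive evidence. Keep the no-adjustment policy, but label the nine results exploratory and report the false-win chance with them: about 13% to 18% when one drug adds nothing and the other has a large effect, 2% to 3% when neither works, at most about 20%. If the Table 5-15 footnotes or other text not in this copy already name these contrasts, confirm it and cite the place.

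The cost is SAP wording and contrast statements on a model already planned, with no new data or patients. The downside is precision. Cell SEs are 2.0 times (versus AGN-190584 alone) and 2.4 to 3.7 times (versus AGN-199201 alone) that of a dose-specific M6 contrast, or 2.45 and 2.9 to 4.5 times that of a pooled one. With 40 per group, the difference detectable at 80% power is 2.80 × 0.2236 ≈ 0.63 SD between patients and 0.34 to 0.52 SD within patients (0.67 and 0.37 to 0.56 SD with 35 completers). A combination better than both components by 0.63 SD passes both contrasts with 76% to 80% power.

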7.3.1 Primary Efficacy Analyses

For the primary efficacy analysis, the weighted average change from baseline will be analyzed using a mixed model with treatment group, dosing period, baseline UNVA, and iris color as fixed effects.

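### Do M6 and M7 need a stated rule for coding the fixed-combination periods?

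*SAP*

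**What the plan says.** SAP 4.1 counts 17 treatment combinations, 16 unfixed and one fixed, and gives the fixed combination to every patient in one of the five dosing periods. SAP 5.1.1.1.2 lists 17 treatment groups; one entry is "Fixed Combo + Fixed Combo". Protocol 1.4 puts the fixed combination at pilocarpine 1% and oxymetazoline 0.125%, the doses of one unfixed cell, and explains that it is there for bridging.

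In SAP Table 5-3, M6 is a mixed model "controlling for factors (pilocarpine dose, oxymetazoline dose) and covariates (baseline UNVA severity, iris color", and its tests are "P-values from contrast t-test comparing active AGN-199201 treatment groups vs AGN-199201 vehicle". M7 adds the interaction of the two doses: "controlling for fixed factors (pilocarpine dose, oxymetazoline dose,), covariates (baseline UNVA severity, iris color), and interactions (pilocarpine dose and oxymetazoline dose interaction". M8 is defined as "Plot of CFB LS means and SE bars for each treatment group".

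SAP 5.1.1.1.3 adds that "Individual endpoint analyses may specify exceptions (additions or deletions) to these general definitions". In Table 5-15 the row "Average change from baseline in UNVA letters (Primary efficacy variable" carries note marks 2 and 3 on CFB MMRM and CFB ANCOVA. The text of those notes is not in the public copy.

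Protocol 7.3.1 says the primary variable "will be analyzed using a mixed model with treatment group, dosing period, baseline UNVA, and iris color as fixed effects". The Protocol Summary describes the same analysis as a response surface approach, and Protocol 7.5 sizes the study for a response surface model.

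**The concern.** Two dose factors at their nominal levels define 4 × 4 = 16 cells, while the SAP defines 17 treatments. The seventeenth shares its doses with one of the 16, so dose alone cannot tell them apart, and the visible M6 and M7 text does not say how its periods enter.

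If they were pooled by nominal dose, the unfixed 1% / 0.125% cell, a candidate for the optimum, would consist mostly of fixed-combination data, and the bridging comparison would be lost. If the list label were read as a separate level of both dose factors, the usual marginal LS means could not be estimated. The protocol's treatment-group term, read as the 17 listed groups, would have avoided both, and SAP 5.2.2 does not mention a move to dose factors.

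**Working it through.** **Inputs.** Protocol 7.5: 4 groups, 5 sequences per group, 8 patients per sequence. Protocol 1.4: three active concentrations of each drug, to which vehicle adds a zero level. SAP 4.1: 17 treatments.

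**Counts.**
- Treatments: 4 × 4 + 1 = 17, as the SAP states.
- Patients: 4 × 5 × 8 = 160. Patient-periods: 160 × 5 = 800.
- Fixed combination: 160 periods (160/800 = 20%). Each unfixed treatment: 40.
- Nominal 1% / 0.125% cell if pooled: 40 + 160 = 200 periods, of which 160/200 = 80% are fixed combination.

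**Estimability.** With design matrix X, a linear function l of the parameters is estimable when l(X'X)⁻(X'X) = l. Marginal LS means weight the levels of the other factor equally. Rank is for the treatment part only. Covariates, a period term and the compound-symmetry matrix do not alter which functions are estimable. Each entry gives rank, then estimable marginal LS means.

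| Coding of fixed-combination periods | M6 | M7 | Fixed mean separate? |
|---|---|---|---|
| Nominal doses | 7; 8 of 8 | 16; 8 of 8 | No |
| Excluded | 7; 8 of 8 | 16; 8 of 8 | No estimate |
| Own level of both factors | 8; 0 of 10 | 17; 0 of 10 | Yes |
| Own pilocarpine level, oxymetazoline 0.125% | 8; 9 of 9 | 17; 5 of 9 | Yes |
| Own oxymetazoline level, pilocarpine 1% | 8; 9 of 9 | 17; 5 of 9 | Yes |
| Own oxymetazoline level, group's pilocarpine dose | 8; 9 of 9 | 20; 9 of 9 | Yes, but pilocarpine mislabelled in 3 of 4 groups |
| Nominal doses plus fixed/unfixed indicator | 8; 8 of 8 | 17; 8 of 8 | Yes |

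The 0 of 10 arises because the fixed level of pilocarpine and the fixed level of oxymetazoline occur only together, so their columns are identical. Every marginal mean then needs one of those effects without the other, or in a different proportion. The 17 treatment means do not: all 17 are estimable in both M6 and M7 under that coding. So are M6's three contrasts of unfixed active oxymetazoline against vehicle. The contrast lost in M6 is the fixed level against vehicle.

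**Size if pooled or separated.** The documents give no within-patient correlation, so 0.3, 0.5 and 0.7 are assumed, with cyclic sequences, period effects, compound symmetry and no dropout. Under nominal-dose pooling the M7 estimate for 1% / 0.125% moves from the unfixed mean by 0.83, 0.85 and 0.86 of the true fixed-minus-unfixed difference, which is unknown. With the indicator, the standard error of that difference is 0.16, 0.14 and 0.12 SD in M7 and 0.13, 0.12 and 0.10 SD in M6.

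**The case for a change.** The strongest argument for a change is that the coding decides the output. Across the seven codings above, two give no separate fixed-combination estimate, and three of the other five leave M7's marginal LS means incomplete. Protocol section 3 describes the study as comparing unfixed combinations with a fixed one, and Protocol 1.3 says the programme aims at a fixed-dose product. One sentence would remove the doubt at no cost in data. It stands that the visible wording has no coding rule and that the choice has consequences.

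Three parts do not stand.

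- The codings do not force a choice between losing the fixed estimate and losing M6's marginal LS means. Four of the seven keep both.
- The 0-of-10 result depends on reading an entry in a treatment list as a model specification. A 17-level treatment factor fits that list equally well, and the SAP does not say that M6's LS means are marginal.
- Dose factors with an interaction are a natural way to carry out the response surface approach the protocol already calls for, so it is not clear that SAP 5.2.2 had a change of model to record.

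**Conclusion.** No change to the plan is needed. This is missing detail that an analyst would fill sensibly. SAP 5.1.1.1.2 makes the fixed combination one of 17 treatment groups and M8 asks for an LS mean for each. SAP 4.1 also uses the term treatment groups for the four parallel arms, but the defined list has 17 entries. Nominal-dose coding or exclusion yields only 16 unfixed-dose cells, so the shortfall would show as soon as the outputs were built. A separate level in both factors would show itself through non-estimable marginal means. A fixed/unfixed indicator or a 17-level treatment factor is an ordinary programming choice and gives all 17 means.

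The stated objective and hypotheses concern concentrations and combination against monotherapy, with no fixed-versus-unfixed test promised. The harmful case, a shift of 0.83 to 0.86 of an unknown difference, requires a pooling rule the SAP nowhere states and rests on the assumed correlations. The notes to Table 5-15 sit on exactly these two analyses and SAP 5.1.1.1.3 permits additions there, so the rule cannot be called absent from the full plan. The estimability results depend only on the design and the coding, not on the assumed correlations.
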